**Figure 3: Graphical presentation of study plan**

### 9.3 Recording of target parameters

- Determination of flow profile of the A. femoralis communis and A. poplitea by CCDS
- Determination of ABI
- Assessment of walking distance by standardized treadmill examination (3km/h with 12% inclination)
- Determination of clinical PAD stage according to Fontaine and Rutherford
- Non-invasive in-vivo measurement by MSOT

- Determination of relevant clinical data: Age, Sex, risk factors for PAD, underlying diseases, previous operations and current medication
  - *These target values are either available in the electronic patient file or they are collected at presentation for the study.*

## 9.4 Total study duration

Corresponding to the number of patients, the expected total duration of the study until the inclusion of the last patient is approximately 12 months. Participation in the study takes approximately 1.5 hours per participant. For patients with PAD approximately 70 minutes are spent on examinations and transport, which only arise from participation in the study. Only one examination time point per patient will be needed.

# 10 Risk-benefit analysis

## 10.1 All study related risks

Based on the classification criteria for medical devices (Directive 93/42/EWG, Annex IX), the optoacoustic system of iThera Medical corresponds to Class IIa:

- Active diagnostic device
- Non-invasive
- Temporary use (<60 min)

No CE certification is available for this research device (current type designation according to imprint: Acuity Echo). A conformity assessment procedure in the sense of the MPG is not intended or planned by the manufacturer as of now. It is therefore a purely scientific study. There is no dependency on the manufacturer; all diagnostic and analytical procedures are available to the study directors on site.

### ***Adherence to energy levels***

The laser safety and maximum permitted radiation dose for irradiation with laser pulses is regulated in the laser standards ANSI and IEC 60825. The MSOT system meets these standards and therefore remains below the MPE (maximum permissible exposure) limits for skin irradiation and is therefore considered safe

### ***Temperature increases due to MSOT in tissue***

Optoacoustic imaging does not result in any significant temperature increase in the tissue. The absorption of a laser pulse in the tissue results in a local transient temperature increase of a few millikelvin. Depending on the duration of the examination and the skin type of the participant, temperature increases occur typically in the range of less than one degree Kelvin.

### ***Histological changes in tissue***

Histological changes in the target tissue and surrounding structures are neither expected nor have they been observed in previous preclinical and clinical studies.

Slight, reversible redness or warming might occur in very sensitive skin.

Such side effects are to be noticed at any time by the test person or doctor; the examination can then be interrupted or aborted. In any case, no irreversible damage is to be expected.

In general, the near infrared light used in the MSOT can lead to retinal damage if the eye is irradiated. In order to prevent this, test participants and examiners will wear appropriate laser safety glasses during the examination.

Since the data obtained is not used to interpret diagnostic results, there is no risk of possible misdiagnosis or incorrect display of data in this exploratory scientific study.

There are no further risks within the scope of this study, nor were additional risks observed based on the assessment of preliminary data.

### **10.2 Benefits associated with the study**

The data obtained in the studies can provide essential information about the blood circulation and perfusion of the musculature in patients with PAD. It is therefore possible that these diagnostic procedures can be used in the future to better detect non-invasively critical blood flow situations and to derive therapy indications. Especially in groups of patients who can only be assessed inadequately or not at all using classical diagnostic methods.

### 10.3 Termination criteria

#### ***Termination criteria for the individual participant:***

Participation in the study is discontinued if the skin becomes conspicuously warm or reddened. The examination time per anatomical region is limited to 5 minutes, so that these events are very unlikely.

In addition, participation in the study will be terminated if the above described muscle exercises between the two MSOT measurements cannot be performed, e.g. due to dyspnea, orthopedic disorders, etc.

Due to the short duration of the study participation, no other discontinuation criteria are planned.

#### ***Termination criteria for the whole study:***

Termination of the entire study must be declared if significant and unobserved serious adverse health effects, which have not been known or observed so far, occur as a result of the MSOT investigation. This is considered unlikely, since more than 200 patients or test persons have already been examined with this method at the University Hospital Erlangen alone.

Otherwise, a termination of the entire study is not planned.

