The actual current walking distance is used to classify the severity of PAD and will be recorded by a treadmill examination. Under medical supervision, the participants should walk the maximum possible distance on the treadmill at a 12% incline and 3 km/h (standard setting). Should the participant not be able to manage the incline, it will be reduced to 6%. Should that also be impossible, the incline will be reduced to 0%. The walking distance is measured in meters. Since the first 200 meters are of particular importance for the classification of PAD, the study physician terminates the examination when the walking distance exceeds 500 meters. The treadmill examination lasts about 15 minutes and is exclusively part of the study participation; it is not part of the vascular surgical routine diagnostics.

All examinations mentioned above take place in the vascular surgery department. Since the MSOT device is located in the endoscopy rooms of the internal medicine center, the participating persons are transported there by wheelchair after the previously mentioned examinations. It is important that no physical exercise is exerted during transport, as this could falsify the MSOT values. The transport takes about 15 minutes. Afterwards, the examination is performed in the area of the M. triceps surae (in patients in this area of the affected leg) with the MSOT device.

The MSOT examination is performed analogous to a sonography over the corresponding skin layers without further invasive procedures. The anatomical region can be localized by means of built-in B-image sonography; the corresponding optoacoustic signals can then be derived from this. The duration per anatomical region is limited to 5 minutes; participants can remain in a relaxed position during the examination; assistance in the form of breathing maneuvers or similar is not necessary. The position of the transducer is marked with a skin pencil so that the subsequent measurement can be taken over the same region of the muscle. Afterwards, the participant has to complete a defined walking distance of 150 meters, which takes place under medical supervision. This is followed by another measurement of the M. triceps surae using the MSOT. The pilot study showed that active muscle exercises between the two MSOT examinations causes a change in the perfusion parameters and may possibly unmask a stenosis in the lower leg area.

[figure not shown]

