## 8.4 Baseline Variables

- Age
- Gender
- Affected leg/examined leg
- Risk factors for PAD (Smoking, arterial hypertension, lipid abnormalities, diabetes mellitus, obesity, positive family history)
- Relevant underlying diseases (CHD, CHF, atrial fibrillation, CKD, carotid artery stenosis, previous cerebrovascular event)
- Previous surgery or interventions on the arterial vessels of the lower extremity
- Current medication
- Date of last angiography

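### The protocol's risk section leaves out exertion, and its whole-study stopping rule does not reach the study-only treadmill test or serious exertional effects of a known type

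*Protocol*

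**What the plan says.** **Exercise.** Protocol 9.2 sets two bouts. The first is a treadmill test: "Under medical supervision, the participants should walk the maximum possible distance on the treadmill at a 12% incline and 3 km/h". The incline can drop to 6% or 0%, and "the study physician terminates the examination when the walking distance exceeds 500 meters". The test is not routine care: "The treadmill examination lasts about 15 minutes and is exclusively part of the study participation". The second comes between the two MSOT scans. It is a supervised 150 m walk that can be shortened, or replaced by standing or seated foot exercise, and it is also done only for the study.

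**Risk.** Protocol 10.1, headed as covering all study-related risks, deals with laser energy, tissue warming, skin and histological effects, eye exposure and misdiagnosis. It then concludes: "There are no further risks within the scope of this study, nor were additional risks observed". Section 10.4 puts the overall risk at an extremely low level, citing previous experience and the fact that only the limbs are measured.

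**Stopping.** Under Protocol 10.3 the whole study must end if serious adverse health effects "which have not been known or observed so far, occur as a result of the MSOT investigation". The section closes: "Otherwise, a termination of the entire study is not planned". For the individual, participation ends if the skin becomes conspicuously warm or red, or if the between-scan exercise cannot be done, with dyspnea and orthopedic problems as examples.

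**Population.** SAP 8.4 records these conditions at baseline: "Relevant underlying diseases (CHD, CHF, atrial fibrillation, CKD, carotid artery stenosis, previous cerebrovascular event".

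**The concern.** The documents themselves make exertion risk foreseeable. The patients have symptomatic arterial disease up to rest pain and tissue loss, the SAP expects cardiac and cerebrovascular disease to be worth recording, and 10.3 names dyspnea as a reason why exercise may fail. A section that claims to be complete, and then denies any further risk, is at odds with a study-only uphill walk to each participant's limit.

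Two things are at stake. The risk-benefit assessment rests on an incomplete list. And if serious events occurred on the treadmill, even repeatedly, nothing in the written plan would call for a study-level review.

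**Working it through.** The point is textual. The only arithmetic describes exposure.

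**1. Is exertion among the listed risks?** Section 10.1 has five items: laser energy, tissue warming, skin and histology, eye, misdiagnosis. None is exertion. Both grounds given in 10.4 concern the measurement, and neither mentions the exercise. The more than 200 prior examinations cited in 10.3 are of the MSOT method, so they say nothing about treadmill testing.

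**2. How much of the study-only time is the treadmill?** Inputs from Protocol 9.2: duplex sonography about 10 min, treadmill about 15, transport about 15, MSOT session about 30.

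10 + 15 + 15 + 30 = 70 min

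This reproduces the figure in Protocol 9.4: "approximately 70 minutes are spent on examinations and transport, which only arise from participation in the study". The treadmill share is 15/70 = 21%. The 30-minute MSOT session also contains the second exercise.

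**3. How demanding is the walk at most?** Speed: 3 km/h = 3000 m / 60 min = 50 m/min. Climb = L × sin(arctan(grade)).

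| Distance | Time | Climb at 12% | Climb at 6% | Climb at 0% |
|---|---|---|---|---|
| 200 m | 4 min | 23.8 m | – | – |
| 500 m (stop) | 10 min | 59.6 m | 29.9 m | 0 m |

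The 500 m row is a ceiling that many stage IIb-IV patients would probably not reach. These figures measure exposure, not risk.

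**4. Which serious exertional effects does the whole-study rule reach?** The rule sets two conditions: the effect must be previously unknown, and it must result from the MSOT investigation. Section 9.2 times the between-scan activity together with both scans and treats the whole as one examination. The treadmill test is a separate examination, done in the vascular surgery department before transport to the MSOT device.

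| Source | Previously unknown effect | Known type of effect |
|---|---|---|
| Between-scan exercise | Arguably covered | Not covered |
| Treadmill test | Not covered | Not covered |

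Three of the four cells are empty. The rule also treats the two bouts unevenly: on this reading, a previously unknown serious effect of the between-scan exercise would oblige termination, while the same effect on the treadmill would meet no criterion.

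**The case against.** The strongest reply is that participants are already protected. Both walks are medically supervised, and the treadmill runs at a standard setting with a reducible incline and a 500 m stop. The between-scan exercise steps down through 100, 50 and 25 m to standing and then seated movement. The study physician can exclude anyone on safety grounds (8.1), and consent can be withdrawn at any time (9.1). The treadmill also comes before the between-scan exercise, so a treadmill event that rules out further exercise already meets the individual criterion in 10.3. All of this stands, and no new individual-level criterion is needed. But these measures act on one participant at a time. They neither state exertion as a risk nor provide a study-level response.

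A second reply is that the MSOT investigation includes the between-scan exercise. Section 9.2 supports that reading, so a reader who infers that the rule covers no exertional event at all goes too far. The reading does not extend to the treadmill or to effects of a known type.

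A reader might also infer that the study could not be stopped, or that participants are not told about exertion. The documents support neither. Saying that termination is otherwise not planned does not forbid it, and the consent form was not available for this review.

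Finally, the harm cannot be sized: SAP 8.4 is a list of baseline variables with no prevalence, and no event rate is given. That stands, and it limits the severity.

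**Conclusion.** The point holds as a minor safety and documentation matter. Section 10.1's statement that no further risks exist is wrong on the protocol's own description of the procedures, and 10.4 rests on the same omission. The whole-study rule leaves out the treadmill test and every serious exertional effect of a known type. Whether it covers unknown effects of the between-scan exercise depends on how widely the MSOT investigation is read.

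The exposure is about 15 of 70 study-only minutes, and at most 10 minutes of walking with about 60 m of climb. The number of participants who might be harmed cannot be estimated. The conclusion rests on the wording of sections 9.2 and 10 alone. No endpoint, threshold or analysis is affected.

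**What to change.** 1. In Protocol 10.1, replace the denial of further risks with a statement that the treadmill test and the between-scan exercise carry exertion risk. Make 10.4 consistent with it.
2. In Protocol 10.3 (whole study), keep the MSOT sentence and add: *Serious adverse health effects of any study-only procedure, including the treadmill and between-scan exercise, whether or not previously known, prompt review and, if warranted, termination of the study.*

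The added sentence leaves the decision to judgement. What it gains is a written requirement to review. Clinical thresholds are for the investigator and the ethics committee.

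The cost is a protocol wording amendment, with no new procedures or staff. The downsides are a less favourable risk statement and possibly a matching line in the participant information.

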### 10.4 Statement on medical justifiability

Based on previous experience in adults the risk of occurrence of unwanted events is stratified as extremely low. In this study no central organs are examined, but only extremities are measured – this leads to a further significant reduction of a possible residual risk.

## 11 Biometrics, results pilot study

### 11.1 Explorative study: explanation of the statistical methodology, justification of the selected number of cases

#### ***Results pilot study***

The pilot study included seven patients. One leg with collateralized superficial femoral artery occlusion (group: “*occlusion*”) and the contralateral leg with open superficial femoral artery (group: “*open*”). The macrocirculation parameters examined showed a significant difference between the two groups (Ankle-Brachial Index). Transcutaneous examination of the M. triceps surae was possible in all cases using the MSOT procedure. Oxygenated hemoglobin (oxyHb) and total hemoglobin (totalHB) were found to be suitable parameters. Both active and passive muscle loading in the form of walking load and passive muscle loading (Whobbler©), respectively, showed a strong influence on muscle perfusion. This effect was more pronounced in the case of long-distance occlusive A. femoralis superficialis. After active walking, the “*open*” group showed a significant increase in the parameters (totalHB p=0.028, oxyHB p=0.028). This effect was not significant in the “*occlusion*” group (totalHB p=0.176, oxyHB p=0.398).

## **12 Data management and data protection**

### **12.1 Data acquisition and storage**

All raw data, such as patient files, are source documents. Their availability is ensured for routine monitoring. The participation of the individual patients or test persons in the study is documented. The study leader maintains an independent list for the identification of the participating patients. This list contains the names and date of birth as well as the date of examination and pseudonymization codes of the patients and subjects. The study leader is responsible for the quality of data collection and storage. The data storage (complete data) takes place on computers or specially designed network drivers of the University Hospital Erlangen.

### **12.2 Pseudonymization**

Prior to a scientific analysis of the materials and data of this study, all information will be pseudonymized according to the guidelines of the Bundesdatenschutzgesetz (Federal Data Protection Act).

### **12.3 Data transfer**

A transfer of the data or biological material is not intended in this study and will not take place; in particular, the manufacturer will not have access to the data. The study

results can be published anonymously, whereby it will not be possible to draw conclusions about the identity of the participating persons. The data will be kept for ten years and then will be destroyed.

#### **12.4 Revocation, data deletion**

If the declaration of consent is revoked, data collection up to this point can be taken into account. The patient has the right to demand that the data be destroyed, provided that legal provisions do not prevent such destruction.

### **13 Dealing with Random Findings in Healthy Subjects**

The collection of all findings as well as the evaluation of the ABI and the images from the FKDS, are only for the purpose of this study and not for general or specific diagnostics. Evidence of a disease unknown to the subject may escape detection in these examinations. If abnormal findings are discovered during the scientific evaluation, a corresponding specialist will be consulted for the review and reporting of the values and images originally determined for research purposes. Whether a reportable finding is present is decided by the study leader according to his best judgment. The test person will be informed in advance about any disadvantages of a report in the written declaration of consent.

Such disadvantages are to be understood as such:

- Strong psychological stress due to the knowledge or suspicion of a threatening disease
- Disadvantages of certain legally significant acts, such as the conclusion of a life or health insurance policy or an employment contract
- Further examinations linked to the notification of findings that may pose a health risk, even if further processing means that the findings have no disease value.

After clarification with regard to the above-mentioned possible disadvantages caused by the notification of random findings within the framework of this study, the test person will inform in writing whether or not he/she wishes to be informed and advised about such abnormalities.

## **14 Handling of biomaterials**

No biomaterials are obtained.

## **15 Insurance**

A separate proband insurance is taken out under an annual contract with the insurer HDI Global SE, Düsseldorf Representative Office. The insurance is based on the agreements in accordance with the „Versicherung für nicht der Versicherungspflicht unterliegende klinische Prüfungen“(Insurance for clinical trials not subject to obligatory insurance).

## 1 Version History

Version	Changes	Authors
1.1	See summary_of_changes_SAP.pdf	PD Dr. med. [name], [name], [name]

## 2 List of Abbreviations and Definition of Terms

AAA .....	Siehe abdominal aortic aneurysm
ABI .....	Siehe Ankle-Brachial Index
CCDS .....	Siehe color-coded vascular duplexsonography
CFA .....	Siehe Common femoral artery
CHD .....	Siehe coronary heart disease
CHF .....	Siehe chronic heart failure
CIA .....	Siehe common iliac artery
CKD .....	Siehe chronic kidney disease
CLTI .....	Siehe chronic limb threatening ischemia
DGA .....	Siehe Deutsche Gesellschaft für Angiologie (German Society for Angiology)
EIA .....	Siehe external iliac artery
Hb .....	Siehe deoxygenated hemoglobin
HbO 2 .....	Siehe oxygenated hemoglobin
Hbtot .....	Siehe total hemoglobin
IIA .....	Siehe internal iliac artery
MSOT .....	Siehe Multispectral Optoacoustic Tomography
PAD .....	Siehe Peripheral arterial occlusive disease
PSV .....	Siehe Peak-Systolic-Velocity
SFA .....	Siehe superficial femoral artery
TASC .....	Siehe Trans Atlantic Intersociety Consensus
TS .....	Siehe triceps surae muscle

## 3 Introduction

### 3.1 Preface

PAD is one of the most common diseases of the elderly. As life expectancy increases, there is a need for new treatment concepts and new diagnostic procedures.

Up to now, only the measurement of macrocirculation in the form of the CCDS, the ABI and the measurement of the actual walking distance are available as independent validation measures of revascularization methods (endovascular/open). The S3 guideline for diagnosis, therapy and medical aftercare of PAD published in 2015 by the DGA recommends aftercare in the sense of

clinical examinations, especially for patients after vascular surgery. For the validation measures already mentioned, however, there are not infrequent patient groups for which these methods provide only insufficient or unusable results (e.g. diabetes mellitus, terminal renal failure). In these cases, independent verification of the success of the therapy performed would have to be performed using angiography (digital subtraction angiography, CT angiography or MR angiography). However, this is not routinely performed in the respective patient populations due to the associated risks (including radiation exposure, contrast agent administration, invasiveness).

MSOT now provides a new non-invasive diagnostic option that may be able to fill this diagnostic gap. The technique is based on the photoacoustic effect whereby energy by means of light flashes is applied to the tissue. This leads to a constant change of minimal expansion and contraction (thermoelastic expansion) of individual tissue components or molecules. The same examination unit can then detect the resulting sound waves. In the newly configured device (Acuity Echo, iThera Medical GmbH, Munich, custom-made), an extended spectrum of laser light can be used, which ultimately enables not only the detection of hemoglobin and its oxygenation levels, but also the detection of other markers such as collagen and lipid. As hemoglobin concentration and oxygenation status are markers for perfusion, MSOT-based imaging of these parameters could be a highly sensitive and reliable method to analyze muscle perfusion.

The aim of this cross-sectional study is to define an independent parameter using the MSOT method, which allows a statement about the current perfusion situation of the lower extremity and correlates with the angiography, which is considered the gold standard. For this purpose, patients of different PAD stages, who have already been routinely examined in angiography in advance, will be included. In parallel, we will investigate a healthy control group, whereby these volunteers do not need a prior angiography. A validation of the results will be performed on a group of patients and healthy volunteers to be examined and analyzed afterwards.

